### 9.6.4 Exploratory Analyses

The exploratory analyses will be conducted using both the FAS and the PPS. Descriptive statistics as described in 9.1.3 will be provided, unstratified, and also using the stratification factors displayed in section 9.1.1. All data (collected and derived) will be listed.

#### 9.6.4.1 Exploratory Objective 1: Additional BoExp

The statistical analyses described in 9.6.1 and 9.6.2 will be repeated using the BoExp listed in Table 3 (without success criteria). Endpoints are assumed to be log-normally distributed, and the natural logarithm of the values will be used (the statistical model will then use the natural logarithm of the baseline as covariate). The results will then be transformed back to the original scale as was done for the BoExp used in the context of the evaluation of the primary and key secondary objectives.

#### 9.6.4.2 Exploratory Objective 2: Comparison with SA

The comparison of the SA arm against CIG and P4M3 (CA35 and CM35 arms combined and separately) on BoExp listed in Table 1, Table 2, and Table 3 will be covered by the statistics computed in sections 9.6.1, 9.6.2, 9.6.3.1, and 9.6.4.1.

#### 9.6.4.3 Exploratory Objective 3: Nicotine/Tobacco Product Use

The exploratory objective 3 related to the nicotine/product use will be covered by the statistics computed as described in section 9.5.

#### 9.6.4.4 Exploratory Objective 4: ABOUT – Product Experience

Data from each item of the ABOUT – Product Experience questionnaire will be summarised as categorical (each possible level per item will be displayed). Subscales will be considered as continuous and summarized accordingly.

#### 9.6.4.5 Exploratory Objective 5: Human Puffing Topography

Separately for each Day = 1, 2, 3, 4, and 5, the per-day parameters (Table 5) will be considered as continuous variables and summarised as described in section 9.1.3 on the P4M3 arm (CA35 or CM35 combined and separately), except that no change from baseline can be computed.

For each subject, the per-day parameters (Table 5) will be averaged over days 1-5. These averages per subject will then be considered as continuous variables and summarised as described in section 9.1.3 on the P4M3 arm (CA35 or CM35 combined and separately), except that no change from baseline can be computed.

---

#### 9.6.4.6 Exploratory Objective 6: CYP1A2 Enzymatic Activity

In this study, the CYP1A2 enzymatic activity will be calculated using the molar ratio of PX and CAF, as described in section 5.5.

The statistical analyses described in 9.6.1 and 9.6.2 will be repeated using the CYP1A2 enzymatic activity expressed as % as endpoint (no logarithmic transformation will be performed). Because CYP1A2 enzymatic activity will only be measured at baseline and Day 5, the REPEATED statement in the model becomes irrelevant and will not be included. Similarly, the terms Day and Arm\*Day in the MODEL statement will be removed and the LSMEANS statement will use Arm instead of Arm\*Day.

#### 9.6.5 Safety Evaluation

##### 9.6.5.1 Adverse Events

AEs (including SAEs) will be collected from the time of ICF signature until the EOS for each participant (AEs occurring on subjects who are not part of the SAF will only be listed and are not part of the summaries related to SAF).

Any AEs which may occur during the screening period will be captured by the investigational site staff and assessed by the Investigator or designee(s) to establish relationship to study procedures.

During a 3-day Safety follow-up period new AEs/SAEs will be recorded and ongoing AEs/SAEs will be followed-up by the study site.

Information recorded for AEs/SAEs will include verbatim description, start and stop dates and times, seriousness, severity (intensity), causal relationship with IP and study procedures, action taken with IP (e.g., reduced, not changed), other action taken (e.g., treatment administered, if led to the subject's discontinuation from the study), and outcome (e.g., resolved, stabilized).

All safety data will be provided in listings by randomized study arm or a group of enrolled but not randomized subjects, subject, and safety period. The safety periods are defined as:

- Screening: from Screening visit to baseline
- Exposure: from Day 1 to Day 5 11:00 PM or early discontinuation date and time
- Follow-up: from end of exposure to end of Safety follow-up

Unless otherwise specified, summaries will be produced by randomized study arm or a group of enrolled but not randomized subjects and safety periods.

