**Figure 1 Study Design**

#### Confidentiality Statement

Data and information contained in this document are considered to constitute trade secrets and confidential commercial information, and the legal protections provided to such trade secrets and confidential information are hereby claimed under the provisions of applicable law. No part of this document may be publicly disclosed without the written consent of Philip Morris Products S.A.

- Screening period (from Day -30 until Day -3):

The screening period covers up to four weeks prior to admission. A presentation of P4M3 (without product use) will be done by the site staff during the Screening visit. All subjects will receive information on the risks of smoking and smoking cessation advice. Eligible subjects will return to the investigational site for verification of eligibility.

- Admission (from Day -2 until morning of Day -1):

On Day -2 (admission), after all inclusion/exclusion criteria are checked, all eligible subjects will be enrolled and perform a product test using both P4M3 variants: tobacco flavor “Classic Auburn” 3.5% nicotine (CA35) and menthol flavor “Classic Menthol” 3.5% nicotine (CM35), with an *ad libitum* use regimen for a duration of approximately 10 minutes *ad libitum* use per flavor. After the product test, subjects not willing to use P4M3 during the study will be discontinued and will be replaced. Subjects willing to continue participation will start their confinement period. CIG smoking will be allowed *ad libitum* from the time of admission of the subject until approximately 11:00 PM, except before/during assessments requiring smoking breaks. Use of any TNP other than CIG (and P4M3 for the product test) will not be allowed after admission.

Provided that the 28-day Screening period is not exceeded, alternate subjects (not yet randomized) have to repeat the admission visit of the following group to re-confirm their eligibility for randomization.

- Baseline (from Day -1, 06:30 AM until Day 1, 06:29 AM):

Subjects may continue smoking their CIG *ad libitum*, except before/during assessments requiring smoking breaks. The 24-hour urine collection for Day -1 will start in the morning of Day -1 (urine collection details provided in Appendix A of the protocol). Baseline assessments will be performed as indicated in Appendix A of the protocol.

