#### **Confidentiality Statement**

---

Data and information contained in this document are considered to constitute trade secrets and confidential commercial information, and the legal protections provided to such trade secrets and confidential information are hereby claimed under the provisions of applicable law. No part of this document may be publicly disclosed without the written consent of Philip Morris Products S.A

---

- Non-compliance to the study procedures based on the judgment of the Investigator
- Violation of eligibility criteria

Subjects who will be discontinued from the study before enrolment will be replaced. After enrollment but before randomization, subjects who will be discontinued from the study will enter the 3-day Safety follow-up period and will be replaced (except alternate subjects). In general, subjects that are discontinued after randomization will not be replaced. Should there be the need to discontinue all subjects from one cohort, e.g., all subjects suspected to have contracted a disease pathogen, subjects for a replacement cohort may be enrolled and randomized.

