### 8.4 Safety Set (SAF)

The Safety Set (SAF) population will consist of all the subjects with at least one exposure to P4M3 (product test at Admission Day -2), and who have at least 1 valid value for a safety assessment. The SAF will be analyzed according to randomized study arm or a group of enrolled but not randomized subjects when applicable (there is an exception to this rule and mis-randomized subjects will be assigned to their actual exposure arm, see [Table 12](#)).

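### The SAP's safety periods put adverse events that follow the Day -2 P4M3 product test together with events from before any P4M3 use

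*SAP*

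**What the plan says.** SAP 9.6.5.1 (Adverse Events) defines three periods:

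- The first is "Screening: from Screening visit to baseline".
- The second covers use of the assigned product. It opens on Day 1 and closes at 11:00 PM on Day 5, or sooner if the subject discontinues early.
- The third takes over where the second stops: "Follow-up: from end of exposure to end of Safety follow-up".

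Summaries are to be produced by these periods, with enrolled-but-not-randomized subjects as a reporting group alongside the four arms. SAP section 7 lists the end of Exposure and the start of Follow-up as clarifications of the protocol. It says nothing about the boundary between Screening and first product use.

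The study design in SAP 4.1 divides the same calendar differently. It has a "Screening period (from Day -30 until Day -3"), then Admission on Day -2, then "Baseline (from Day -1, 06:30 AM until Day 1, 06:29 AM"). At Admission, "all eligible subjects will be enrolled and perform a product test using both P4M3 variants", for about 10 minutes per flavor.

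SAP 8.4 builds the Safety Set on that test: "all the subjects with at least one exposure to P4M3 (product test at Admission Day -2"), provided a valid safety value exists. Randomization is not required.

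Subjects who leave before randomization are covered in SAP 4.5.3: "After enrollment but before randomization, subjects who will be discontinued from the study will enter the 3-day Safety follow-up period". SAP 4.6.1 gives the same follow-up to alternates who are never randomized.

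**The concern.** A by-period AE table is read as a before-and-after display: Screening is background, Exposure is time on product. Here the background column also contains the hours after each subject's first contact with the test product. Protocol 2.3.3 expects transient symptoms of mild nicotine overdose as a possible effect of P4M3. An acute reaction to first use would be tabulated in the same column as events from weeks before it.

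Safety and tolerability is the secondary objective, and SAP 9.6.5.1 makes AEs its primary assessment. The group that did not go on to randomization matters most here. It includes subjects who declined to continue after trying the product, and the product test is their only P4M3 use in the study. For them the by-period table has no column that isolates events after use.

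**Working it through.** The plan gives no figure to reproduce. The check is whether the three periods divide the calendar cleanly around first P4M3 use.

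**Inputs**

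- Exposure starts at Day 1 06:30 (SAP 4.6.1). Take this as hour 0. There is no Day 0.
- Baseline runs from Day -1 06:30 (hour -24) to Day 1 06:29 (SAP 4.1).
- The product test is on Day -2 (SAP 4.1, 8.4). Its clock time is not given, so a range of 08:00 to 20:00 is assumed. Day -2 06:30 is hour -48, so 08:00 is hour -46.5 and 20:00 is hour -34.5.
- Each AE is assumed to be placed in a period by its start time, which SAP 9.6.5.1 says is recorded.

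**Step 1. Product test to start of baseline.** This time is Screening on any reading.

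- Test at 08:00: -24 - (-46.5) = 22.5 hours.
- Test at 20:00: -24 - (-34.5) = 10.5 hours.

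**Step 2. The baseline window.** Its length is 0 - (-24) = 24 hours. If Screening runs to the end of baseline, these 24 hours are Screening too. If it runs to the start of baseline, they lie after Screening and before Exposure, in no period.

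**Step 3. Total per randomized subject, product test to Day 1 06:30.**

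- Test at 08:00: 22.5 + 24 = 46.5 hours.
- Test at 20:00: 10.5 + 24 = 34.5 hours.

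This is for a single Admission. Alternates may repeat Admission with a later group within the 28-day screening limit (SAP 4.1; Protocol 9.2.1, footnote). For them, the time between first P4M3 use and Day 1 can be longer.

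**Step 4. Subjects who never reach Day 1.** Exposure would run from hour 0 to the time of discontinuation, which comes earlier. Two illustrations:

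- Discontinuation on Day -2 at 14:00: end minus start = -40.5 hours.
- Discontinuation on Day -1 at 20:00: end minus start = -10.5 hours.

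The interval is empty in both cases. Follow-up starts at the end of that empty interval. If the early-discontinuation clause is applied regardless, Follow-up starts at discontinuation and the 3 days can be counted. If it is not, no start is defined.

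**The case against.** The case against making much of this is a good one, and most of it stands.

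- **The events are not lost.** SAP 9.6.5.1 tabulates AEs overall as well as by period. It also tabulates them by relatedness to product, expectedness, severity and action taken, and it lists all safety data. A product-test AE can be found there. A reader might infer that these events vanish from the safety report; the documents do not support that.
- **They should not simply move into Exposure.** All four arms take the product test before randomization, including the cigarette and abstinence arms, and all subjects may smoke on Day -2 and Day -1. Keeping these events apart from the assigned product is right. What remains at fault is the Screening label and the merging with events before first use.
- **Non-randomized subjects are not without a follow-up period.** That stronger reading is tempting, because Exposure starts on a day they never reach and the protocol's glossary limits early termination to the time after exposure has started. But SAP 4.5.3 counts any enrolled subject who does not complete as discontinued, and names unused alternates among the reasons. The early-discontinuation clause can therefore be read to cover them. Their AEs before baseline also have a period, namely Screening. What is missing is a clear statement.
- **Day -1 is not certainly unassigned.** Because Exposure follows directly from Day 1, reading Screening as running through the end of baseline is at least as natural as the other reading.
- **Causality is still assessed.** For screening-period AEs, SAP 9.6.5.1 mentions only the relationship to study procedures. One might infer that product-test AEs escape a product-causality judgment. Protocol 8.2.4 requires that judgment for each reported AE.
- **One subject in an arm of 18 is 1/18 = 5.6 percentage points.** That is the weight of any one subject. It does not estimate how many events are misplaced, and moving an event between periods leaves an arm's overall incidence unchanged.

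**Conclusion.** The point holds for the by-period display. The rule as written counts AEs between first P4M3 use and baseline with AEs from before any use, although the Safety Set is defined by that use and the design ends screening at Day -3. Day -1 is ambiguous between Screening and no period. The start of Follow-up for non-randomized subjects has to be inferred.

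Of the 34.5 to 46.5 hours affected per randomized subject, 10.5 to 22.5 are labelled Screening on any reading and 24 depend on the meaning of baseline. The range rests on the assumed test times and a single Admission. The definition applies to everyone in the Safety Set, but only subjects with an AE starting in that interval change a table, and the documents give no basis for predicting how many.

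Safety is descriptive in this study. Type I error, power, and the primary and key secondary analyses do not change. This is a correction worth making to a stated rule, limited to one set of tables.

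**What to change.** Amend SAP 9.6.5.1, and record the change in section 7:

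1. **Screening** ends just before the subject's first P4M3 product test.
2. **Product test/baseline** (new) runs from the first product test to Day 1 06:29, or to discontinuation for subjects never randomized. It is kept separate from randomized Exposure and summarized for the whole Safety Set. For alternates who repeat Admission, it starts at their first product test, so the time between Admissions falls here too.
3. **Exposure** keeps its present end and starts at Day 1 06:30.
4. **Follow-up** keeps its present rule, with an added statement that for enrolled-but-not-randomized subjects it starts at discontinuation.

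AE start dates and times are already recorded, so no new data are needed. The cost is the SAP wording and one extra period in the AE tables. The table shells are a separate document, so the work there is inferred.

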#### Confidentiality Statement

---

Data and information contained in this document are considered to constitute trade secrets and confidential commercial information, and the legal protections provided to such trade secrets and confidential information are hereby claimed under the provisions of applicable law. No part of this document may be publicly disclosed without the written consent of Philip Morris Products S.A.

---

Adverse event data will be used for the primary assessment of safety. Other safety variables monitored in this study will include vital signs (systolic and diastolic blood pressure, pulse rate, respiratory rate), ECG data, spirometry data, clinical chemistry, hematology, urine analysis safety panel, concomitant medications.

The number and percentage of subjects with AEs and SAEs will be tabulated by the Medical Dictionary for Regulatory Activities (MedDRA) system organ class (SOC) and preferred term (PT) for the SAF, overall and by safety period. The number of AEs and SAEs by relatedness to product exposure (including expectedness) and relatedness to study procedures, AEs by severity, and AE by action taken related to the product will be summarized. The number of subjects experiencing an event and the number of events for the SAF will be tabulated. Common adverse events will also be tabulated. Common AEs would be those AEs that have PTs with incidence  $\geq 5\%$  in any of the randomized study arms or group of enrolled but not randomized subjects.

Unless specified otherwise, results will be sorted alphabetically by SOC, and by decreasing frequency of the PTs within a SOC. In the event of PTs having equal frequencies, the PTs will be sorted alphabetically within the SOC.

#### 9.6.5.1.1 Serious Adverse Events (Including Deaths)

The number and percentages of SAEs will be summarized overall and by SOC and PT for each randomized study arm or a group of enrolled but not randomized subjects when applicable, for the SAF. Tabulations will include both the number of subjects experiencing an event and the number of events.

Unless specified otherwise, results will be sorted alphabetically by SOC, and by decreasing frequency of the PTs within a SOC. In the event of PTs having equal frequencies, the PTs will be sorted alphabetically within the SOC.

The number and percentage of deaths will be presented if applicable and AEs leading to death will be listed.

All SAE data will be listed.

#### 9.6.5.1.2 Adverse Events Leading to Discontinuation

Subjects discontinuing the study due to an AE will undergo the early termination procedures and will enter the 3-day Safety Follow-Up Period. If there are any AEs leading to discontinuation of a product or the study, they will be summarized overall and by SOC and PT for the SAF.

#### Confidentiality Statement

---

Data and information contained in this document are considered to constitute trade secrets and confidential commercial information, and the legal protections provided to such trade secrets and confidential information are hereby claimed under the provisions of applicable law. No part of this document may be publicly disclosed without the written consent of Philip Morris Products S.A.

---

All AEs leading to discontinuation will be listed.

### 9.6.5.2 Device Events

The number and percentage of subjects with device events, the number and percentage of subjects with device events overall, leading to an AE, an SAE, discontinuation, or to non-adherence will be tabulated for the SAF.

All device events will be listed.

### 9.6.5.3 Medications, Physical Findings, Vital Signs and Other Observations Related to Safety

#### 9.6.5.3.1 Clinical Laboratory Evaluation

Table 14 details the clinical laboratory parameters.

**Table 14 Clinical Laboratory Parameters Safety Panel**

Hematology	Clinical Chemistry	Urine Analysis
- Hematocrit	- Albumin	- pH
- Hemoglobin	- Total protein	- Bilirubin
- Mean corpuscular hemoglobin	- Alkaline phosphatase	- Glucose
- Mean corpuscular hemoglobin concentration	- Alanine aminotransferase	- Nitrite
- Mean corpuscular volume	- Aspartate aminotransferase	- Red blood cell traces
- Platelet count	- Blood urea nitrogen	- Protein
- Red blood cell count	- Creatinine	- Specific gravity
- White blood cell (WBC) count	- Gamma-glutamyl transferase	
- Differential WBC count:	- Fasting glucose*	
• Neutrophils	- Lactate dehydrogenase	
• Basophils	- Potassium	
• Eosinophils	- Sodium	
• Lymphocytes	- Total bilirubin	
• Monocytes	- Direct bilirubin	
	- Total cholesterol	
	- Triglycerides	

Descriptive statistics for actual values and changes from baseline will be produced for the clinical chemistry, hematology, and urinalysis safety panel, for the SAF.

All laboratory data will be listed for all subjects.

#### 9.6.5.3.2 Medical History and Concomitant Disease

Medical history (any condition that started and ended prior to the ICF signature at the Screening visit) and concomitant diseases (any condition detected or ongoing at the time of ICF signature) will be coded using MedDRA and listed separately.

Medical history and concomitant diseases will be summarized by randomized study arm or a group of enrolled but not randomized subjects, SOC and PT for the SAF. The number and percentages of subjects with any medical history/concomitant disease will be presented along with the number and percentage of subjects who record each medical history/concomitant disease by SOC and PT. Unless specified otherwise, results will be sorted alphabetically by SOC, and by decreasing frequency of the PTs within a SOC. In the event of PTs having equal frequencies, the PTs will be sorted alphabetically within the SOC.

Medical history and concomitant disease data will be listed for all subjects.

#### 9.6.5.3.3 Prior and Concomitant Medication

All medications will be listed for all enrolled subjects by randomized study arm or a group of enrolled but not randomized subjects when applicable using PT and Anatomical Therapeutic and Chemical (ATC) codes (WHO Drug Global). A flag will be included in the listing to indicate whether the medication is prior or concomitant.

Concomitant medications will be summarized by randomized study arm or a group of enrolled but not randomized subjects for the SAF. The number and percentages of subjects who used the medication at least once will be presented by ATC 1st and 2nd levels and preferred drug name.

#### 9.6.5.3.4 Physical Examination

The number and percentage of subjects with normal, abnormal not clinically significant and abnormal clinically significant results will be tabulated for the SAF.

Physical examination data will be listed for all subjects.

#### 9.6.5.3.5 Vital Signs

Actual values and changes from baseline for pulse rate (bpm), systolic blood pressure (mmHg) and diastolic blood pressure (mmHg), respiratory rate (breaths/min), and body temperature (°C) will be summarized as continuous variables (see section 9.1.3) for the SAF.

Vital signs data will be listed for all subjects.

---

